10.10.8 Exposition of the Clinical Investigation Plan

In case of translation of the Clinical Investigation Plan into the language of the participating countries, the English version is to be considered as the original; i.e., when expounding the contents of the Clinical Investigation Plan in these languages, the English version is definitive in case of doubt.

11.0 Bibliography

Please reference the Clinical Investigator Brochure for a complete literature review and evaluation.

APPENDIX B
Written Procedures for Monitoring Investigations

Written Procedures for Monitoring Clinical Investigations

A. Selection of the monitor.

Designated by the sponsor to oversee the investigation, the monitor may be an employee of Cook, an employee of a monitoring organization (CRO) or an independent contractor or consultant. The monitor shall be qualified by training and experience to monitor the investigation in accordance with all applicable regulations and standards for conducting clinical investigations.

B. General duties of the monitor.

The monitor must ensure that the investigation is conducted in accordance with:

1. The signed investigator agreement.
2. The Clinical Investigation Plan (CIP).
3. Any conditions imposed by the IRB/EC or regulatory authority.
4. The requirements of the applicable regulations and standards.

C. Reports by the monitor to the sponsor.

1. Any noncompliance with the items listed above. In the event that the investigator is not complying with the requirements outlined above, it is the sponsor's responsibility to secure compliance.
2. Any adverse events or effects that are potentially reportable to a regulatory authority.

D. Initiating the investigation.

Prior to initiating any clinical use of the device, the monitor will participate in a pre-investigation or initiation visit with each investigative site.

At a minimum, the following items shall be addressed during the site initiation visit:

- Provide training to investigator on his/her responsibilities per the investigator agreement, applicable laws, regulations and standards; and
- Provide training to investigator that the IRB/EC approval letter and informed consent/patient information is on file before initiation of the clinical investigation.

Additionally, training may be provided to the investigator on:

- The regulatory status of the device/product(s) and the requirements for the accountability of same;

- The nature of the clinical investigation plan (CIP);
 - The requirements for an adequate and well-controlled clinical investigation;
 - His or her obligation to obtain informed consent in accordance with applicable regulations;
 - His or her obligation to ensure continuing review of the clinical investigation by the IRB/EC in accordance with conditions of approval and applicable regulations and to keep the sponsor informed of such IRB/EC approval and subsequent IRB/EC actions concerning the investigation;
 - The importance of access to an adequate number of suitable subjects to conduct the investigation;
 - The importance of adequate facilities for conducting the clinical investigation; and
 - The importance of sufficient time from other obligations to carry out the responsibilities to which the investigator is committed by applicable regulations.
- E. During the course of the investigation, at the direction of the Project Manager, the monitor should visit the site frequently enough to ensure that:
- The facilities and research staff used by the investigator continue to be acceptable for purposes of the clinical investigation;
 - The applicable version of the CIP and agreements are being followed;
 - Changes to the CIP, informed consent/patient information have been approved by the IRB/EC and/or reported to the sponsor and the IRB/EC;
 - Accurate, complete, and current records are being maintained;
 - Accurate, complete, and timely reports are being made to the sponsor and IRB/EC; and
 - The investigator is carrying out the agreed-upon activities and has not delegated them to other previously unspecified staff.
- As appropriate, the following tasks could be performed during periodic visits:
- Device/product accountability review;
 - Adverse event review to ensure that events are appropriately reported within the time periods required by the sponsor, CIP, IRB/EC, and applicable regulatory requirements; and
 - Source data verification per the monitoring plan to determine that :
 - Informed consent/patient information has been documented in accordance with applicable regulations and expectations of local IRB/EC;

- The information recorded in the case report forms (paper or electronic) is complete, accurate, and legible;
- There are no omissions in the case report forms (CRFs) of specific data elements, such as the administration to any patient of concomitant test articles or the development of an intercurrent illness;
- Missing visits or examinations are noted; and
- Subjects failing to complete the clinical investigation and the reason for each failure are noted.

F. Records of the monitor.

The monitor shall prepare and maintain records of each initiation visit and each periodic visit, general site contact, or discussion. These will include:

1. Date, name and address of the investigator, and names of other staff members present at each meeting.
2. A summary of the findings of the visit.
3. A statement of any action taken by the monitor or investigator to correct any deficiencies noted.
4. The monitor shall immediately notify the sponsor of any conditions of non-compliance with the Clinical Investigations Plan, conditions of IRB/EC or regulatory authority approval, or the applicable regulations.

APPENDIX C
Definitions

Calcification: Landing zone and iliac calcification will be graded based upon the following:

None:	Lack of calcification;
Mild:	Less than 40% circumferential calcification;
Moderate:	40-70% circumferential calcification; or
Severe:	Greater than 70% circumferential.

Clinical Utility Measures: Number of blood transfusions; Ventilator days; Days to resumption of oral fluids; Days to resumption of normal diet; Days to resumption of normal bowel function; Duration of ICU stay; Days to discharge.

Disabling Chronic Obstructive Pulmonary Disease: Forced expiratory volume (FEV₁) < 1.0 liter or receiving home oxygen therapy.

Dissection Grade:

Acute:	Within 14 days of onset;
Subacute:	Between 15 days and 30 days of onset; or
Chronic:	Between 31 days and 90 days of onset.

Embolization: Clinical evidence of ischemic tissue remote from the operative field, caused by air, thrombus dislodged from the aneurysmal sac, aortic neck, and/or false lumen, including those tissues supplied by vessels in the head, renal arteries, aortic visceral branches, pelvic vessels, and vessels of the upper and lower limbs. This is, of course, distinct from pre-operative, operative or post-operative intentional embolization procedures (e.g., to treat Type II entry-flow).

Entry-flow: Contrast-enhanced blood entering the false lumen for one or more of the following reasons:

Type I entry-flow: Entry-flow caused by peri-prosthetic flow at the proximal and/or distal seal zones;

Type II entry-flow: Entry-flow caused by retrograde flow from patent collateral vessels into the false lumen through the primary tear;

Collateral entry-flow: Entry-flow caused by retrograde flow from collateral vessels directly into the false lumen;

Type III entry-flow: Entry-flow caused by a defect in the graft fabric, inadequate seal (between covered graft components only), or disconnection of covered graft ancillary components;

Type IV entry-flow: Entry- flow caused by graft fabric porosity, often resulting in a generalized blush of contrast within the false lumen; or

Unknown entry-flow: Entry-flow through undefined origin.

Left Ventricular Ejection Fraction: The measurement of the left ventricular function in the resting state. The normal LVEF ranges between 55% and 80% (mean = 67%).

Major Adverse Events: - Myocardial infarction, chronic renal insufficiency/chronic renal failure requiring dialysis, bowel ischemia, stroke, paraplegia or paraparesis, and prolonged (> 72 hours) ventilatory support.

Malperfusion: Malperfusion in the setting of an aortic dissection is defined as one or more of the following¹:

1. Visceral hypoperfusion by an acute abdomen, abdominal pain out of proportion to physical examination findings in setting of radiographic hypoperfusion of mesenteric bed, lactic acidosis attributed to visceral malperfusion, or need for bowel resection.
2. Renal hypoperfusion including oliguria or anuria in setting of rising renal function tests (creatinine or blood urea nitrogen) or radiographic evidence of impaired renal artery blood flow.
3. Lower extremity hypoperfusion indicated by abnormal pulse examinations in conjunction with leg pain, pallor, paresthesias or paralysis.
4. Spinal cord hypoperfusion as noted by altered motor function of one or both of legs attributed to a possible spinal cord source.

MI (Non-Q-Wave): Clinical evidence of a myocardial infarction with elevated peak CK values greater than three times the upper limit of normal with elevated CK-MB (above the institutions upper limit of normal) in the absence of new pathological Q-waves or clinical evidence of a myocardial infarction with troponin greater than three times the upper limit of normal, as determined by the investigator.

MI (Q-Wave): Post-procedure chest pain or other acute symptoms consistent with myocardial ischemia and the presence of new pathological Q-waves in two or more contiguous ECG leads.

Migration (radiographic): Antegrade or retrograde movement of the proximal or distal components of the endoprosthesis > 10 mm relative to anatomical landmarks identified on the first post-operative CT scan as evaluated by core laboratory.

Migration (clinical): Antegrade or retrograde movement of the proximal or distal components of the endoprosthesis resulting in the need for a secondary intervention.

New York Heart Association Classification:

1. Patient with cardiac disease but without resulting limitations of physical activity. Ordinary physical activity does not cause undue fatigue, palpitation, or dyspnea.
2. Patients with cardiac disease resulting in slight limitation of physical activity. They are comfortable at rest; ordinary physical activity results in fatigue, palpitation or dyspnea.
3. Patients with cardiac disease resulting in marked limitation of physical activity. They are comfortable at rest; less than ordinary physical activity causes fatigue, palpitation or dyspnea.
4. Patients with cardiac disease resulting in inability to carry out any physical activity without discomfort. Symptoms of cardiac insufficiency may be present even at rest. If any physical activity is undertaken, discomfort is increased.

Occlusive Disease of iliacs: Occlusive disease will be graded based upon the following:

- | | |
|-----------|---|
| None: | Lack of occlusive disease; |
| Mild: | Some disease, focal with less than 30% narrowing; |
| Moderate: | Between 30-50% narrowing not requiring interventional techniques to meet inclusion criteria; or |
| Severe: | Greater than 50% or any patient requiring angioplasty prior to endograft delivery. |

Pain/Symptoms rating:

None:	No pain/symptoms;
Mild:	Nagging, annoying, interfering little with activities of daily living (ADLs);
Moderate:	Interferes significantly with ADLs; or
Severe:	Disabling; unable to perform ADLs.

Resistant Hypertension: arterial pressure > 140/90 mm Hg despite use of three antihypertensive medications. (Kaplan NM. Resistant hypertension. Journal of Hypertension 2005; 23: 1441-1444.)

Renal Failure: Acute or progressive renal insufficiency leading to the need for dialysis or hemofiltration.

Reversible ischemic neurologic deficit (RIND): Clinically significant central nervous system deficit lasting > 24 hours and < 72 hours.

Renal Insufficiency: A rise in serum creatinine of more than 30% above the pre-procedure level, resulting in a serum creatinine level > 2.0 mg/dl that does not spontaneously resolve (does not include those patients with a pre-procedure serum creatinine > 2.0 mg/dl).

Rupture: Rupture in the setting of aortic dissection is defined by the presence of hemorrhage outside the aortic boundaries, which is noted on CT scans.¹

Stent/attachment system fracture/break: Fracture or breakage of any portion of the stent or attachment system including metallic fracture or breakage of any suture material used to construct the stent or secure the stent or attachment system to the graft material.

Stroke: Permanent, clinically significant central nervous system deficit.

Tortuosity of iliac arteries: Tortuosity will be graded based upon the following:

None:	Lack of tortuosity;
Mild:	Fairly straight arteries;
Moderate:	Angulation manageable with stiff wires, < 70 degrees; or
Severe:	Angulation difficult, may require surgical exposure for straightening, not straightened entirely with wires.

Transient Ischemic Attack (TIA): Central nervous system deficit lasting \leq 24 hours.

Type B Aortic Dissection: Thoracic aortic dissection with the most proximal extent of dissection distal to the left subclavian artery.

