5.5.1 Inclusion Criteria

A patient is deemed suitable for inclusion in the study if the patient has an acute, complicated, Type B aortic dissection with at least one of the following characteristics (see Appendix C, Definitions):

- 1) Aortic rupture; or
- 2) Branch vessel obstruction/compromise resulting in malperfusion

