7.0 Statistical Considerations

7.1 Sample Size Calculations

The study is designed to enroll 67 patients to evaluate the safety and effectiveness hypotheses (Section 3.3).

For the primary safety endpoint, based on the data from the combined physician-sponsored studies¹, the rate of freedom from 30-day major adverse events (see Appendix

C, Definitions) was estimated to be 61.2%. With a clinically relevant non-inferiority margin of 10%, a performance goal of freedom from 30-day MAE was established to be 51.2%. Sixty patients will be necessary to assess the primary safety hypothesis, under an expected rate of freedom from 30-day MAE at 69.2% (estimated from an on-going clinical trial with the Zenith® Dissection Endovascular System in patients with complicated, type B aortic dissection), with a one-sided exact binomial test, at a type I error rate of 0.025 and a power of 0.8.

For the primary effectiveness endpoint, based on the data from the combined physician-sponsored studies, the survival rate at 30 days was estimated to be 89.4%. With a clinically relevant non-inferiority margin of 10%, a performance goal for 30-day survival was established to be 79.4%. Forty patients will be necessary to assess the primary effectiveness hypothesis, under an expected 30-day survival rate of 94.9% (estimated from an on-going clinical trial with the Zenith® Dissection Endovascular System in patients with complicated, type B aortic dissection), with a one-sided exact binomial test, at a type I error rate of 0.025 and a power of 0.8.

Cook intends to enroll 73 patients, to allow for additional patients who may withdraw or be lost to follow-up, and to account for six previously enrolled patients that would not be eligible for enrollment based on the clarifications provided in Version 4 of the CIP (i.e., patients who were ASA class V or who were without confirmed absence of bowel necrosis at the time of enrollment). While the data from all 73 patients enrolled in the study will be reported, the primary safety and effectiveness hypotheses will be assessed based on the 67 patients enrolled according to the inclusion/exclusion criteria specified in Version 4 of the CIP.

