9.3 Adverse Event Reporting

Events known to be related to pre-existing conditions or existing at admission are not considered adverse events (e.g., prior medically-treated cardiac arrhythmia with no change in status during the endovascular procedure). Additionally, common standard of care practices are not considered adverse events (e.g., centers located at high geographical altitudes that discharge all patients on home oxygen therapy regardless of procedure).

All adverse events (i.e., device-related and non-device-related) are to be reported using the appropriate case report form (Adverse Event/Complication form). In cases of adverse device effects (adverse event with relation to the study device) or serious adverse events, completed forms should be submitted to the Data Coordinating Center immediately upon knowledge of the event.

Cook Research Incorporated
[name]

[name]
[contact]
[contact]

The Data Coordinating Center will notify the sponsor accordingly. In accordance with applicable requirements, the investigator will notify the local Ethics Committee/IRB, while the sponsor will notify the regulatory authority. Furthermore, if the sponsor determines that the device presents a potential risk to the study patients, all investigators in the study will be notified. Refer to section 8.1 for a list of potential adverse events related to this study.

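### Patients with pre-procedure creatinine above 2.0 mg/dl cannot meet the renal insufficiency definition however far they worsen, although renal malperfusion is a route into the study

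*Combined protocol and SAP*

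**What the plan says.** **Definition.** Appendix C (Renal Insufficiency) requires "A rise in serum creatinine of more than 30% above the pre-procedure level, resulting in a serum creatinine level > 2.0 mg/dl", and the rise must also not resolve spontaneously. A closing parenthesis adds that the definition "does not include those patients with a pre-procedure serum creatinine > 2.0 mg/dl". No other rule is given for those patients.

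**Entry.** Section 5.5.1 lists two qualifying characteristics, aortic rupture and "Branch vessel obstruction/compromise resulting in malperfusion". Appendix C gives four forms of malperfusion. The renal form begins "Renal hypoperfusion including oliguria or anuria in setting of rising renal function tests (creatinine or blood urea nitrogen"; it can also be met on imaging evidence of impaired renal artery flow. None of the 30 exclusion criteria in Section 5.5.2 sets a limit on creatinine, eGFR or dialysis.

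**Primary safety endpoint.** The MAE list in Appendix C has one renal item: "chronic renal insufficiency/chronic renal failure requiring dialysis". Renal failure is defined separately as "Acute or progressive renal insufficiency leading to the need for dialysis or hemofiltration", with no creatinine exemption written into it.

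**Pre-existing conditions.** Section 9.3 states: "Events known to be related to pre-existing conditions or existing at admission are not considered adverse events".

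**The concern.** An exemption for raised baseline creatinine is natural in an elective population with stable chronic kidney disease. In this study a raised pre-procedure creatinine can be part of the acute presentation. The rule then treats similar patients very differently. An unresolved rise from 1.9 to 2.5 mg/dl meets the definition. An unresolved rise from 2.1 to 5.5 mg/dl without dialysis does not.

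Nothing in the plan takes exempt patients out of the analysed 67. The natural reading is that they are counted as free of this event, although the plan does not say how they are scored. At stake is whether new renal harm after the procedure is visible in patients who arrive with impaired kidneys and, on one reading of the MAE list, whether the primary safety rate is biased in favour of the device.

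**Working it through.** **Step 1. What the exemption removes.** Relative rise = (later value / pre-procedure value) − 1.

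- 1.9 to 2.5 mg/dl: 2.5/1.9 − 1 = 31.6%. This is above 30% and ends above 2.0, so it counts if unresolved.
- 2.1 to 5.5 mg/dl: 5.5/2.1 − 1 = 162%. This passes the same tests but is exempt.
- Without the exemption, a patient at 2.1 would have to exceed 2.1 × 1.30 = 2.73 mg/dl. A stable high baseline would still not count, because the rise is measured from the patient's own value.

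**Step 2. Whether another rule restores these events.**

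- Section 9.3 removes conditions present at admission. It does not add later worsening back.
- The renal failure definition picks up exempt patients who need dialysis or hemofiltration. Some doubt remains, because it is worded in terms of renal insufficiency and might import the exempted definition.
- An unresolved worsening without dialysis is restored by neither rule.

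**Step 3. Two readings of the MAE item.**

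| Reading of the dialysis qualifier | Is an unresolved creatinine rise without dialysis an MAE? | Effect of the exemption on freedom from MAE |
|---|---|---|
| Governs both renal terms | No, for any patient | Small or nil |
| Governs renal failure only | Yes, if not exempt | Can bias the rate upwards |

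Both renal terms also carry the word chronic, which is not defined for a 30-day endpoint. The text does not settle which reading applies.

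**Step 4. Reproducing the plan's own figure.** Inputs from Section 7.1: performance goal 51.2% (61.2% − 10%), expected rate 69.2%, tested "with a one-sided exact binomial test, at a type I error rate of 0.025 and a power of 0.8", 60 patients needed and 67 in the hypothesis test. The pass mark r is the smallest number of event-free patients with P(X ≥ r | n, 0.512) ≤ 0.025.

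- n = 60: r = 39, type I error 0.0216, power at 69.2% 0.802. The stated 60 is reproduced.
- n = 67: r = 43 (43/67 = 64.2%), type I error 0.0220, power 0.847.

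**Step 5. Illustration under the second reading.** Suppose that the rate with every renal event counted is exactly 51.2%, and that on average k patients of 67 have an uncounted renal event and no other MAE. The recorded rate is then 0.512 + k/67, and the chance of passing is P(X ≥ 43 | 67, 0.512 + k/67).

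| k | Recorded rate | Chance of passing |
|---|---|---|
| 0 | 51.2% | 0.022 |
| 1 | 52.7% | 0.038 |
| 2 | 54.2% | 0.063 |
| 3 | 55.7% | 0.100 |

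The values of k are assumptions. The documents give neither the share of patients above 2.0 mg/dl before the procedure nor their rate of renal worsening.

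**The case against.** **The benchmark may use the same rule.** The 51.2% goal is a published rate less 10 points. If the source exempted the same patients, the goal is already on that scale, the test as planned is not inflated, and dropping the exemption only from the new data would count against the device. This stands. The documents do not show the source's renal rule: the malperfusion and rupture definitions cite that source, while the renal insufficiency definition cites nothing. It is the reason not simply to replace the definition in the primary test.

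**The dialysis qualifier may govern both terms.** This is a plausible reading, and under it the primary endpoint is barely touched. It stands as a condition on the conclusion.

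**The exemption has a rationale.** Creatinine already climbing at presentation may go on climbing because of the presenting injury, and Section 9.3 keeps conditions present at admission out of the adverse events. This is fair as far as it goes. Section 9.3 does not deal with later worsening, however, and the exemption removes all of it, whatever the cause.

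**The affected group may be small.** Renal hypoperfusion is one of four forms of malperfusion, can be met on blood urea nitrogen or imaging, and stands beside rupture as an entry route. Patients enrolled at or below 2.0 mg/dl remain covered, transient rises are left out for everyone, and a patient with another MAE is already a failure. All of this limits the size without removing the gap.

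**No renal endpoint is visible.** The secondary objectives are redacted, so it cannot be said that a separate renal rate is a formal endpoint. The point therefore concerns renal safety wherever this definition is used.

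**Conclusion.** The gap in the definition is real. A patient above 2.0 mg/dl before the procedure cannot meet renal insufficiency however large and lasting the later rise, the study can enrol such patients, and no other rule captures worsening short of dialysis.

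The consequence is conditional. If the dialysis qualifier governs both renal terms, the defect is confined to renal safety reporting. If it governs renal failure only, 30-day freedom from MAE can be biased upwards. The figures of 0.038, 0.063 and 0.100 rest on three assumptions: the second reading, masked events in patients with no other MAE, and a benchmark without the same exemption.

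A reader might infer that the primary safety test exceeds its 0.025 error rate, or that patients enrolled for renal malperfusion as a group escape the renal component. The documents support neither. The first needs the benchmark's rule and the share of exempt patients, which are not given. The second overlooks patients at or below 2.0 mg/dl and those who go on to dialysis. That the exempt patients carry the highest renal risk is a reasonable inference, not something the plan states. The sample size is not in question.

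**What to change.** 1. Prespecify an analysis of renal insufficiency, and of 30-day freedom from MAE, without the parenthetical exemption. A patient above 2.0 mg/dl before the procedure would then count on an unresolved rise of more than 30% from the pre-procedure value.
2. Report it beside the existing definition. Keep the existing definition for the comparison with the 51.2% goal unless the source is shown not to use the exemption.
3. State whether the dialysis qualifier in the MAE list governs one renal term or both, and how exempt patients are scored.
4. Report the number of patients above 2.0 mg/dl at baseline.
5. State that patients on dialysis before the procedure cannot be assessed for the renal component, and that their composite MAE status rests on the other components.

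The cost is a few lines of text and one more derived variable. Table 3 already schedules kidney function tests pre-operatively, post-procedure and at 30 days, so no visits or patients are added. The downside is a little more analysis work and possibly a slightly less favourable safety rate in the added analysis.
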